10.1.2 Reporting of serious adverse events (SAE) and other safety related events

Local investigator responsibilities:

All AESIs should be recorded in the electronic healthcare records and reported in the appropriate eCRF. AEs leading to cessation of trial treatment should be recorded in the relevant section of the eCRF.

SAEs and SARs occurring from the time of randomization until the last FUP visit at day 28 should be reported to the sponsor within 24 hours of the local investigator becoming aware of the event, and assessed by the local investigator as follows:

- **Seriousness:**

When an AE or AR occurs, the investigator responsible for the care of the participant must first assess whether or not the event is serious using the definition given in Table 8. If the event is serious, then the sponsor must be notified within 24 hours.

- **Severity:**

The severity of all reportable events in MYTHIC should be graded as detailed in Table 2 (section 5.2).

- **Causality:**

The investigator must assess the causality of all serious events or reactions in relation to the trial therapy using the definitions in Table 9.

- **Expectedness:**

If there is at least a possible involvement of the trial treatment (or comparator), the investigator should make an initial assessment of the expectedness of the event, however the sponsor has the final responsibility for determination of expectedness. The definition of an UAR is given in Table 8.

The completed SAE form in the eCRF must be signed by the local investigator (or if absent, by a member of the site trial team) and sent within 24 hours of the investigator becoming aware of the event by email to the study center:

[contact]

The minimum criteria required for reporting an SAE are the patient ID, name of local investigator reporting, the event, and why it is considered serious. This initial report must be followed by the completed and signed SAE form in the eCRF within 7 days.

Sponsor responsibilities:

- **SAEs:** All SAEs must be reported immediately and within a maximum of 24 hours to the sponsor of the study. The sponsor will re-evaluate the SAE and return the form to the site. In the case of disagreement with regards to the causality assessment, both opinions will be provided in any subsequent reports. The sponsor is responsible for the reporting of SUSARs and other SARs to the regulatory authorities (Swissmedic) and the CECs, as appropriate.

- **SAEs resulting in death:** All SAEs resulting in death must be reported to the lead CEC via sponsor within 7 days. The other in the trial involved CECs receive SAEs resulting in death in Switzerland via sponsor within 7 days.
- **SUSARs:** A SUSAR needs to be reported to the lead CEC and to Swissmedic via sponsor within 7 days, if the event is fatal, or within 15 days (all other events). The sponsor must inform all investigators participating in the trial of the occurrence of a SUSAR. All in the trial involved CECs will be informed about SUSARs in Switzerland via sponsor according to the same timelines.
- **Safety Signals:** All suspected new risks and relevant new aspects of known adverse reactions that require safety-related measures, i.e., so called safety signals, must be reported to the sponsor within 24 hours. The sponsor must report the safety signals within 7 days to the local CEC and to Swissmedic via sponsor. The sponsor must immediately inform all participating investigators about all safety signals. The other in the trial involved CECs will be informed about safety signals in Switzerland via the sponsor.

Periodic reporting of safety:

An annual safety report is submitted once a year to the local CEC and to Swissmedic via the sponsor.

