5.2 Secondary outcomes

A number of secondary and additional outcomes have been defined as relevant endpoints for antibiotic trials in childhood CAP by the IDSA [62].

2.1: Overall clinical outcome based on benefits and harms (DOOR/RADAR approach)

According to documentation of clinical response (normalization of all VS) and solicited AEs 1x/24h at the end of treatment (day 5) and each FUP visit.

Specific measurement: Documentation of clinical response (normalization of all VS, section 5.1) and solicited AEs (Table 2) 1x/24h at the end of treatment (day 5) and at each FUP visit.

Analysis metric: Desirability of outcome ranking (DOOR) [65].

Method of aggregation: Probability of better DOOR.

Time point: Day 3 (in-hospital visit), day 5 (end of treatment), day 7, 14, 21 (phone calls), and day 28 (close-out visit).

Rationale: The novel *response adjusted for duration of antibiotic risk* (RADAR) methodology utilizes a superiority design [65]. In RADAR, all trial participants are assigned a DOOR. The DOOR is constructed using a 2-step process: (1) categorization of all patients into an overall clinical outcome (Table 3), and (2) ranking participants in the trial using 2 rules: (2a) when ranking the outcomes of 2 patients with different overall clinical outcomes, the patient with a better overall clinical outcome receives a higher rank; and (2b) when ranking the outcomes of 2 patients with the same overall clinical outcome, the patient treated with placebo receives a higher rank. These DOOR ranks are then compared between the treatment arms with regard to the probability of a better DOOR for a randomly selected patient with placebo vs. azithromycin (i.e., Wilcoxon-Mann-Whitney statistic [66]). The DOOR/RADAR approach is helpful for RCTs to define the optimal therapeutic strategy, since considering exclusively the primary endpoint may not allow researchers to accurately balance a proven benefit with other potential harms (i.e., impaired effectiveness or side effects/AEs).

Table 2: Solicited adverse events (AEs) grading [66, 67].

Symptom	Mild (grade 1)	Moderate (grade 2)	Severe (grade 3)
Diarrhea	Looser than normal stools occurring 3-6 times/day	Looser than normal stools occurring >6 times/day	Bloody diarrhea, or diarrhea that requires medical intervention, laboratory testing, or hospitalization
Vomiting	1 episode/day	2-3 episodes/day	≥ 4 episodes/day

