Abdominal pain	Mild or intermittent and does not interfere with daily activity	Moderate or persistent and interferes with daily activity but did not need a medical visit or absenteeism from daily routine	Prevents daily activity and resulted in medical visit or absenteeism
Allergic reaction (rash and/or pruritus)	Localized rash or pruritus without rash	Diffuse rash (maculopapular or urticarial)	Generalized rash consistent with Stevens-Johnson syndrome, erythema multiforme, or toxic epidermal necrolysis; anaphylaxis; or angioedema
Oral/pharyngeal thrush or nappy rash (Candidiasis)	Mild mucocutaneous candidiasis or diaper dermatitis, with no treatment or topical treatment only	Moderate mucocutaneous candidiasis requiring oral antimicrobial treatment	Severe mucocutaneous candidiasis; requires medical intervention, intravenous treatment, or hospitalization

Table 3: Overall clinical outcome.

Outcome	Adequate clinical response*	Solicited AEs**
1	Yes: normalization of all VS	No
2	Yes: normalization of all VS	Mild (grade 1)
3	Yes: normalization of all VS	Moderate (grade 2)
4	Yes: normalization of all VS	Severe (grade 3)
5	No: no normalization of all VS without additional ED or clinic visit or hospitalization	Any grade
6	No: no normalization of all VS with additional ED or clinic visit but without hospitalization	Any grade
7	No: no normalization of all VS with hospitalization (admission, re-admission, or ongoing hospitalization)	Any grade
8	Death (any cause)	

* Adequate clinical response defined by the co-primary outcome normalization of all VS (section 5.1).

** Solicited AEs are defined in Table 3.

2.2: Time (days) to normalization of CAP-related symptoms (i.e., cough, shortness of breath, wheeze, chest pain, sore throat, nasal congestion or runny nose, headache, muscle aches or pains, nausea or vomiting, diarrhea, reduced general condition, decreased appetite, not sleeping well, reduced activity).

Specific measurement: Documentation of symptoms 1x/24h according to a validated measure for childhood respiratory infections [68, 69] by parent and the child until normalization.

Analysis metric: Time to event (days).

Method of aggregation: Hazard/median time to event.

Time point: Time point of resolution of all CAP-related symptoms.

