* The term life-threatening in the definition of a serious event refers to an event in which the patient is at risk of death at the time of the event; it does not refer to an event that hypothetically might cause death if it would be more severe, for example, a silent myocardial infarction.

** Hospitalization is defined as an inpatient admission, regardless of length of stay, even if the hospitalization is a precautionary measure for continued observation. SAE exemptions are hospitalizations for a pre-existing condition that has not worsened or for an elective procedure. These do not constitute an SAE.

*** An example of such an event potentially encountered in MYTHIC is transfer from general ward to ICU.

In MYTHIC, solicited AEs (section 5.2) must be assessed, and if positive, graded at each study visit according to Table 2 (section 5.2) and documented in secuTrial®. SAEs should be followed until resolution or stabilization. Participants with ongoing SAEs at study termination will be further followed up until recovery or until stabilization of the disease after 30 days of termination.

Assessment of causality:

Both investigator and sponsor make a causality assessment of the event to the study drug, based on the criteria listed in Table 9 and in accordance with ICH E2A guidelines [82].

Assessment of severity:

The severity of all symptoms and signs observed during SAEs in MYTHIC should be graded using the solicited AEs grading (section 5.2, Table 2).

Table 9. Criteria for causality assessment of the SAE in accordance with ICE E2A guidelines [82].

Relationship	Description	SAE type
Unrelated	There is no evidence of any causal relationship.	Unrelated SAE
Unlikely	There is little evidence to suggest that there is a causal relationship (for example, the event did not occur within a reasonable time after administration of the trial medication). There is another reasonable explanation for the event (for example, the patient's clinical condition, other concomitant treatment).	Unrelated SAE
Possible	There is some evidence to suggest a causal relationship (for example, because the event occurs within a reasonable time after administration of the trial medication). However, the influence of other factors may have contributed to the event (for example, the patient's clinical condition, other concomitant treatments).	SAR

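### Section 10 makes the five-symptom, three-grade solicited-AE table the severity scale for every SAE, so worsening pneumonia, ICU transfer for respiratory failure and death have no applicable grade

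*Protocol*

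**What the plan says.** Two sentences in the protocol's safety section set the severity scale. Section 10.1.1, under assessment of severity, states: "The severity of all symptoms and signs observed during SAEs in MYTHIC should be graded using the solicited AEs grading (section 5.2, Table 2". Section 10.1.2, in the list of what the local investigator must assess for each SAE or SAR, states: "The severity of all reportable events in MYTHIC should be graded as detailed in Table 2 (section 5.2".

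The table they point to is in section 5.2 and is headed "Table 2: Solicited adverse events (AEs) grading [66, 67". Section 9.2.4.1 says that these solicited events are used to determine DOOR. Its rows are diarrhea, vomiting, abdominal pain, allergic reaction and candidiasis, and its last column is "Severe (grade 3").

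Table 8 in section 10.1.1 counts death, life-threatening events and hospitalization among the criteria for an SAE. Its note on other important medical conditions adds: "An example of such an event potentially encountered in MYTHIC is transfer from general ward to ICU".

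CTCAE appears in the abbreviation list. No safety section in the text shown uses it as a grading scale.

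**The concern.** A list of solicited symptoms has been made the severity scale for all serious events. The list was chosen to capture tolerability, and its rows largely match the effects that section 3.6 attributes to azithromycin. The serious events most likely in children with pneumonia are of another kind: deterioration that leads to admission or intensive care.

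A site that follows the text literally finds no row for such an event. It must leave the grade blank, improvise a meaning for mild, moderate and severe, or grade an incidental listed symptom such as vomiting in place of the event. With 13 centers, different sites may choose differently.

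Severity also has a use beyond description. Table 8 defines an unexpected adverse reaction as one that departs from the product information in its nature or its severity. Expectedness then decides whether a related serious event is a SUSAR.

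**Working it through.** The plan states no figure that could be reproduced, so the check compares the grading rule with the table and with the events the protocol provides for.

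**Step 1: what Table 2 contains.** There are five rows and three grades, with no grade 4 or 5. Each cell is worded for its own symptom. Grade 1 abdominal pain, for example, is "Mild or intermittent and does not interfere with daily activity"; grade 3 diarrhea is "Bloody diarrhea, or diarrhea that requires medical intervention, laboratory testing, or hospitalization"; vomiting is graded by episodes per day. No sentence gives a general meaning of mild, moderate or severe that could be carried to another event.

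**Step 2: set the protocol's own events against the rows.**

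| Event | Where the protocol provides for it | Row in Table 2 |
|---|---|---|
| (Re-)admission for worsening pneumonia | Outcome 1.2 (5.1); hospitalization criterion (Table 8) | None |
| ICU transfer for respiratory failure | Outcome 1.2 (5.1); note to Table 8 | None |
| Death | Table 8; level 8 of the DOOR table (Table 3, 5.2) | No fatal grade in any row |
| Arrhythmia | Described for adults in 3.3 and 3.6 | None |
| Extrapulmonary manifestations | Eight organ groups under outcome 2.5 (9.2.2) | Only the dermatological group overlaps, through the row "Allergic reaction (rash and/or pruritus") |
| Admission for diarrhea or candidiasis; anaphylaxis | Table 8 | Yes, grade 3 |

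So admissions as such are not ungradable. Those caused by a listed symptom have a grade; those caused by the pneumonia do not.

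**Step 3: the unit of grading.** Section 10.1.1 asks for grades of symptoms and signs during an SAE, and section 10.1.2 for the grade of the event. Under 10.1.1 alone, a child admitted with respiratory deterioration who also vomits would receive a vomiting grade and nothing for the deterioration. Neither reading grades the deterioration itself.

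**Step 4: scale.** Inputs from section 11.2: 376 children enrolled and an assumed risk of 5% in each arm for a CAP-related change in care status.

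- Planned case: 376 × 0.05 = 18.8, about 19 children.
- Placebo risk at the 12.5% that the margin would allow, with 5% on azithromycin and 376 / 2 = 188 per arm: 188 × 0.125 + 188 × 0.05 = 23.5 + 9.4 = 32.9, about 33 children.

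Each such event meets an SAE criterion in Table 8, and the underlying pneumonia has no row in Table 2. Section 5.1 describes the expected proportion as at most 5%, so 19 is the upper end of the planning assumption when the arms do not differ.

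**The case against.** The strongest reply is that little depends on the grade. Much of it stands.

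- Harm from withholding treatment is measured elsewhere, by arm: admissions and ICU transfers in co-primary outcome 1.2, failure of vital signs to normalize and death in levels 5-8 of the DOOR table, and extrapulmonary disease in outcome 2.5. The 19 or 33 children counted above are outcome 1.2 events, so none is lost to the safety comparison.
- Seriousness is recorded separately. Death, life-threatening event and hospitalization are distinct criteria in Table 8, the SAE report must say why the event is serious, and the 24-hour duty does not depend on severity.
- A reader might infer that the data monitoring committee, working without formal stopping rules, would see a severity comparison that is informative in one direction only. The protocol does not support this. Section 11.4.5 plans frequencies and types of AEs by arm and the proportion of patients with AEs; section 11.4.3 lists SAEs by arm. No comparison of SAE severity is planned, and the committee's charter is not shown.
- Arrhythmia is not an event the protocol expects in these children. Section 3.3 calls the cardiac risk in children unknown, section 3.6 reports no association with QT prolongation in children, and cardiovascular disease is an exclusion. It is only an example of an unlisted event.

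Two parts do not stand. The first is that sites could apply the column heads generically. The heads do read mild, moderate and severe, but without a general definition each site would set its own thresholds, and life-threatening and fatal levels would still be missing. The second is that no further judgement uses severity. Table 8 brings severity into the definition of an unexpected reaction, and so into SUSAR classification.

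The eCRF parameter list is a separate document. The SAE form may already offer other options, but it would then contradict the protocol.

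**Conclusion.** The point holds as a defect in the protocol's grading rule. Sections 10.1.1 and 10.1.2 prescribe one severity scale for all reportable events, and that scale has no row or level for worsening pneumonia, ICU transfer for respiratory failure, arrhythmia, death or most extrapulmonary disease. This is an instruction that cannot be followed as written, rather than detail left to another document.

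Its reach is limited. About 19 of 376 children would have such an event at the planned 5% risk, and about 33 if the placebo risk were 12.5%. Their events would still be captured, reported within 24 hours and analyzed in outcome 1.2. The loss is consistent severity assessment across 13 centers and a sound severity input to expectedness. It should be corrected, but it does not threaten the primary analyses, DOOR or the detection of serious harm.

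The conclusion assumes that no general severity scale is fixed elsewhere, in the eCRF parameter list or a site manual. Neither is available here.

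**What to change.** Keep Table 2 for solicited AEs and for DOOR. In sections 10.1.1 and 10.1.2, replace the blanket reference with a rule that SAEs and other reportable events outside Table 2 are graded on a general scale that includes life-threatening and fatal levels. CTCAE grades 1-5 would serve, since the term is already in the abbreviation list; another general scale with those levels would do as well. State in both sections whether the grade applies to the event or to its symptoms and signs.

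The cost is two sentences of protocol text, a small change to the severity field in the eCRF, and brief site training. It is best made before SAE data accumulate, because grading in retrospect is less reliable. The sample size and the planned analyses do not change.

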10.1.3 Follow-up of (serious) adverse events

SAEs should be followed until resolution or stabilization. Participants with ongoing SAEs at study termination will be further followed up until recovery or until 30 days after stabilization of the disease termination. FUP should continue after completion of protocol treatment if necessary. A further SAE form, indicated as 'Follow-up' should be completed in the eCRF and sent to the sponsor as information becomes available. The patient must be identified by patient ID only. The patient's name and date of birth should not be used on any correspondence and should be deleted from any test results.

10.2 Assessment, notification and reporting on the use of radiation sources

Not applicable.

11. STATISTICAL METHODS

It should be noted that in this section, the abbreviation HR will be used for hazard ratio and not heart rate.

11.1 Hypothesis

Both co-primary endpoints are compared to show the non-inferiority of placebo to azithromycin, both with a specific non-inferiority margin δ . For the co-primary endpoint **time to normalization of all VS** (time-to-event), for which we will calculate the hazard ratio (HR, as $HR = \text{hazard}_{\text{placebo}} / \text{hazard}_{\text{azithromycin}}$), the null hypothesis (H_0) and the alternative hypothesis (H_1) are as follows:

$$H_0: HR \leq \delta_{HR} \text{ vs. } H_1: HR > \delta_{HR}$$

For the co-primary endpoint **CAP-related change in patient care status** (binary), for which we will calculate the absolute risk difference (ARD, as $ARD = \text{risk}_{\text{azithromycin}} - \text{risk}_{\text{placebo}}$) the null hypothesis (H_0) and the alternative hypothesis (H_1) are as follows:

$$H_0: ARD \leq \delta_{ARD} \text{ vs. } H_1: ARD > \delta_{ARD}$$

The justification of these margins is detailed below (section 11.2).

11.2 Determination of sample size

Sample size calculations were done with regard to the per protocol set (PPS), which includes patients who are positive for *Mp* by PCR (section 6.1, Table 5). To handle multiplicity with two co-primary endpoints, we apply the “at least one” success criterion [83]: We estimated the sample size for both co-primary endpoints at a one-sided significance level (α) of 1.25% (which corresponds to two-sided 97.5% confidence intervals [CI]) and a power of 80% ($\beta=20\%$), and use the larger of the two sample sizes for the trial. This assures a minimum power of 80% to reject at least one null hypothesis.

The primary endpoint **time to normalization of all VS** is considered as a time-to-event endpoint, i.e., the number of days until normalization. Although we expect all patients to normalize VS during the 28-day FUP period, we used an overall event rate of 99% for the sample size calculation, in order to allow censoring. This endpoint will be compared between trial arms by a Cox proportional hazards model to estimate a hazard ratio for placebo vs. azithromycin (a hazard ratio <1 would indicate longer duration to normalization with placebo than with azithromycin). We expect no difference between treatments and thus a hazard ratio of 1. The sample size was estimated to show the non-inferiority of placebo vs. azithromycin treatment in *Mp* PCR-positive patients using the method given in Chow et al. [84] (page 177), with a non-inferiority margin (δ_{HR}) of 0.7 for the HR. Assuming exponential survival times (with an overall event rate of 99% within 28 days), this non-inferiority margin of 0.7 would be equivalent to the inverse ratio of median survival times, which would be 4.8 days for placebo and 3.3 days for azithromycin (with a HR of 1 the median survival time would be 4.2 days). The maximum prolongation of the duration to VS normalization by 1.5 days may be acceptable from a clinical perspective, especially when weighed against side effects, effect of antibiotics on microbiome, increased antibiotic resistance, and costs. These aspects are also discussed for patients with group A β -hemolytic streptococcal pharyngitis, in which modest effects of antibiotics have been observed (symptomatic improvement by only 1-2 days) [85]. Under the assumptions stated above, 302 *Mp* PCR-positive patients are needed for this study (Figure 2). Considering a drop-out rate of 14.5%, 354 patients should be enrolled. This drop-out rate is calculated from an expected drop-out of 10% due to negative *Mp* PCR (false-positive screening by *Mp* IgM LFA, section 6.1, Table 5) and an additional overall drop-out rate of 5% (due to loss to FUP or insufficient compliance), i.e., $0.1 + 0.05 \cdot (1 - 0.1) = 0.145$ (14.5%).

The co-primary endpoint **CAP-related change in patient care status** (binary) will be compared in terms of the absolute risk difference (ARD) between the two arms ($ARD = \text{risk}_{\text{azithromycin}} - \text{risk}_{\text{placebo}}$, $ARD < 0$ would indicate a lower risk with macrolide than placebo). We expect an absolute risk for this unfavorable event of 5% in both trial arms and thus an ARD of 0. The sample size was estimated to show the non-inferiority of placebo vs. macrolide treatment in *Mp* PCR-positive patients, using the method given in Chow et al. [84] (page 90), with a non-inferiority margin (δ_{ARD}) of -7.5% for the ARD (Figure 3). This non-inferiority

would allow a maximum event rate of 12.5% in the placebo arm, which is less than 13.5%, the median acceptable failure rate in treatment of CAP identified in a survey of infectious disease physicians [86, 87]. Under the assumptions stated above, 322 *Mp* PCR-positive patients are needed for this study. Considering a drop-out rate of 14.5% (as above), 376 patients should be enrolled.

As we consider the larger of these two sample sizes (above), 376 patients should be recruited for the trial. We assume that 66.7% of patients agree to screening and study participation (according to [22] and unpublished observations in KIDS-STEP [75] at participating center Zurich) and that 15% of screened patients are *Mp*-positive (section 3.1), which results in 10% of screened patients available for recruiting ($0.67 \times 0.15 = 0.10$).

Thus, we expect that the number of patients to screen is 3,760.

Figure 2. Sensitivity of the sample size for the co-primary endpoint duration to normalization of VS with regard to the non-inferiority margin, δ_{HR} , expecting no difference between treatments (HR=1).

[figure not shown]
[figure not shown]

Figure 3. Sensitivity of the sample size for the co-primary endpoint CAP-related change in patient care status with regard to the non-inferiority margin, δ_{ARD} , expecting no difference between placebo and azithromycin (ARD=0), assuming a probability for a change in patient care status of 0.05.

Based on these considerations, the numbers of enrolled subjects predicted for each trial site is shown in Table 10:

Table 10. The MYTHIC Study timeline with predicted patient enrollment per trial site:

Years	1		2		3		4		5		Total
Months	1-6	7-12	13-18	19-24	25-30	31-36	37-42	43-48	49-54	55-60	
Study phases:											
Preparatory phase	X										
Recruitment		X	X	X	X	X	X	X	X		
Interim analysis					X		X				
Sample size review							X				
Analysis									(X)	X	
Patient recruitment per center:											
Zurich	0	0	8	8	8	9	9	9	9	0	60
Triemli*	0	2**	3	3	3	3	3	3	3	0	23
Winterthur*	0	2**	3	3	3	3	3	3	3	0	23
Basel	0	0	6	6	6	6	6	6	6	0	42
St. Gallen	0	0	3	3	3	3	3	3	3	0	21
Chur*	0	2**	3	3	3	3	3	3	3	0	23
Lucerne	0	0	4	4	4	4	4	4	4	0	28
Aarau	0	0	4	4	4	4	4	4	4	0	28
Bern	0	0	6	6	6	6	6	6	6	0	42
Geneva	0	0	3	3	3	3	3	3	3	0	21
Lausanne	0	0	3	3	3	3	3	3	3	0	21
Fribourg	0	0	3	3	3	3	3	3	3	0	21
Bellinzona*	0	2**	3	3	3	3	3	3	3	0	23
Total	0	8	52	52	52	53	53	53	53	0	376

* 4 centers which are not included in KIDS-STEP [75].

** 6-month set-up phase at the 4 centers not included in KIDS-STEP.

